13.0 Provisions to Monitor the Data to Ensure the Safety of Subjects

- The proposed research is a single-site randomized controlled clinical trial. A Data Safety Monitoring Board (DSMB) will be used. The primary purpose of the DSMB is to ensure the safety of participants and the validity and integrity of data collected during the study. The overall framework involves biannual review of the enrollment/retention, safety and adverse event data, and quality control data by the DSMB during the tenure of the proposed research.

- **DSMB composition:** The DSMB will be composed of three professionals with expertise related to the proposed area of study who are not involved with the study design or experiments. Specifically, the DSMB will include: (1) a board-certified stroke neurologist who also is a stroke recovery researcher and is experienced in care of chronic stroke survivors and their recovery; (2) a registered and licensed occupational therapist who also is a quantitative researcher in outcomes measurement and research design; and (3) a biostatistician with expertise in design and analysis of clinical trials. This multidisciplinary group has experience with management and monitoring of clinical intervention trials involving individuals following stroke, and brings substantial expertise adequate to serve as the DSMB.
- **DSMB responsibilities:**
 - Prior to any enrollment, the DSMB will review the study design, protocol, informed consent documents, amendments, recruitment/enrollment plan, statistical analysis plan, and data and safety monitoring plan, and document the agreement or recommendation.
 - Once the enrollment begins, the DSMB will convene every 6 months to review the progress of the trial.
 - The DSMB will review the enrollment/retention data including new enrollments, progression of the enrollees' participation in the study, any discontinuation of participation in the study with or without adverse events, and the current enrollment status compared to the project time line.
 - The DSMB will review data quality and quality control data.
 - The DSMB will review safety and adverse event data. The DSMB will review the aggregated summary data as well as the individual participants' data (coded). The DSMB will discuss participant risk vs. benefit and other factors that may potentially affect study outcomes. The DSMB will make recommendations for appropriate action to maintain a reasonable safety profile for the study.
 - The DSMB will ensure that all serious adverse events have been followed to resolution, and that the appropriate agencies (including the IRB and/or federal funding agency) have been informed.
 - The DSMB will advise the IRB and the study investigators as to whether the protocol should continue as scheduled or undergo any modification due to findings from the monitoring process. The DSMB may recommend stopping the study early if the study has unanticipated safety concerns that warrant stopping.
 - The DSMB will review study performance as well as make recommendations and assist in resolution of problems reported by the PI.
 - The DSMB will ensure the confidentiality of the study data and the results of monitoring.
 - The DSMB will document their reviews in writing and provide a report to the IRB to summarize oversight activities, recommendations and any concerns regarding participant safety. The report will include participant characteristics (including distributions across race and sex), retention and disposition of study participants, quality assurance issues and reports of adverse events, significant/unexpected adverse events and serious adverse events.
 - The DSMB will review final analysis results upon completion of the data collection.
- **Reporting of safety data:** All serious adverse events will be reported to the IRB as they occur. All enrollment/retention data, and safety and adverse event data will be reported to the DSMB during the review. The DSMB will review the data and submit a report to the IRB. Summative safety data will be reported to VA Research Services, ClinicalTrials.gov, and in publications. As such, we will register this study in ClinicalTrials.gov as soon as the study commences and report results including all adverse events as soon as the study is completed following the guidelines. To protect participants' confidentiality, personally

identifiable information will not be used for reporting. Only de-identified or aggregated data will be used for reporting.

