10.0 Study Design / Methods

- **Study design:** The study will be a randomized controlled trial. Subjects will be randomly assigned to either the experimental or control group using block randomization to ensure balance (half in the experimental, half in the control). Block sizes will be random (4, 6, or 8). The block randomization will be stratified equally by the moderate vs. severe impairment level (with the Fugl-Meyer Upper Extremity assessment cut-off score of 19⁹).
- **Intervention schedule:** All subjects will undergo approximately two-hour force training, 3 times per week for 6 weeks. The experimental group will practice for various target force direction to explore the 3D force workspace and receive explicit feedback in 3D force, while the control group will receive feedback in 1D on a computer screen (in target direction only with no explicit feedback on other directions, thus no training in force directional control, much like simple squeeze ball repetitions). The training dose will be controlled by having a minimum of 8 sets with 14 targets each (a total of 112 targets) per session, with maximum 30 sec allowed for each target (up to 56 min/session).
- **Evaluations:** Outcome measures will be assessed at baseline, immediately after 2 and 4 weeks of force training, at post (within a week after 6-wk force training), and 1 month after training ends (i.e. follow-up to assess retention). The baseline measurement will take place 3 times over 3 weeks prior to training to examine the baseline recovery rate. Each evaluation visit will take 1-5 hours. Evaluation for each outcome is detailed below.

- Behavioral hand function: Subjects' upper extremity function will be assessed using conventional clinical assessments used in occupational/physical therapy in which participants will be asked to move the affected hand and arm, grasp objects and perform prescribed tasks (e.g., lifting an object off the table, releasing the object into a bin, gripping hard, reaching as high or far as possible, opening the hand as much as possible). These tests will be videotaped for scoring. The joint positions and muscle activity during these tasks will also be recorded. The behavioral hand function assessments will last approximately 1 hr.

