15.0 Risks to Subjects

There is a slight risk for loss of confidentiality although researchers will take appropriate steps to protect any information collected about the participants. There is a minor risk of physical and mental fatigue from engaging in the study activity. There is a minor risk of discomfort from having muscle activity sensors or joint position sensors during hand movement during the behavioral hand function assessment. There is a minor risk of skin irritation from adhesives used to affix muscle activity sensors or joint position sensors during the behavioral hand function assessment. There is a risk of fall from standing or walking, although subjects will be wearing a whole body harness to prevent such events. The treatment one person receives may prove to be less effective or to have more side effects than the other study treatment. The experimental treatments may have unknown side effects.

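### Serious adverse events go to the IRB as they occur, but the only stated timing for the DSMB is a six-monthly review, an interval longer than a participant's whole time in the trial

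*Combined protocol and SAP*

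**What the plan says.** Section 13.0 (Reporting of safety data) sets two rules next to each other. For the IRB: "All serious adverse events will be reported to the IRB as they occur". For the DSMB: "All enrollment/retention data, and safety and adverse event data will be reported to the DSMB during the review".

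The timing of the review is given twice in the same section, and the two statements agree: "The overall framework involves biannual review of the enrollment/retention, safety and adverse event data" and "Once the enrollment begins, the DSMB will convene every 6 months to review the progress of the trial".

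On early stopping, section 13.0 (DSMB responsibilities) says: "The DSMB may recommend stopping the study early if the study has unanticipated safety concerns that warrant stopping". The sentence just before it is wider. It has the board advise the IRB and the investigators, on the basis of monitoring findings, whether the protocol carries on unchanged or is modified. Another bullet lets the board recommend suitable action to keep the safety profile reasonable. A further bullet has it help resolve difficulties that the principal investigator brings to it.

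Section 15.0 lists falling among the risks: "There is a risk of fall from standing or walking, although subjects will be wearing a whole body harness to prevent such events".

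**The concern.** Section 13.0 makes participant safety part of the DSMB's primary purpose and makes the board responsible for checking that every SAE is followed to resolution and that the proper agencies have been told. It is also the body for which the plan specifies a stroke neurologist, an occupational therapist and a trial biostatistician. Yet the plan writes an expedited rule for the IRB and a scheduled rule for the DSMB. Followed as written, it can leave the DSMB unaware of an SAE for months, while other participants go on training under the same procedures. A hazard that can recur, such as one tied to the harness or to the move from sitting to standing to walking, is the kind of problem for which early independent review is useful.

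The second, smaller matter is wording. The one sentence on early stopping is framed around unanticipated concerns, whereas falls are a risk the protocol has already named. The neighbouring sentences on the board's remit carry no such limit.

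**Working it through.** The plan gives no figure of its own to reproduce. The check compares the review interval with the length of a participant's stay.

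**Inputs**
- Review interval: 6 months (section 13.0).
- Baseline: 3 weeks. Section 10.0: "The baseline measurement will take place 3 times over 3 weeks prior to training to examine the baseline recovery rate".
- Training: 6 weeks nominal. Section 10.0: "All subjects will undergo approximately two-hour force training, 3 times per week for 6 weeks". Section 14.0 allows withdrawal if training is not finished in 10 weeks, so 10 weeks is taken as the long case.
- Post-training evaluation: within a week after training (section 10.0).
- Follow-up: 1 month after training ends (section 10.0).
- Conversion: 1 month = 365.25 / 12 / 7 = 4.348 weeks.

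**Interval:** 6 × 4.348 = 26.1 weeks.

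**Stay = baseline + training + follow-up**

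| Case | Sum (weeks) | Stay (weeks) | Interval / stay | 1 − stay / interval |
|---|---|---|---|---|
| Nominal | 3 + 6 + 4.348 | 13.3 | 1.95 | 0.49 |
| Training takes 10 weeks | 3 + 10 + 4.348 | 17.3 | 1.50 | 0.34 |
| As above, with the month counted from a post visit one week later | 3 + 11 + 4.348 | 18.3 | 1.42 | 0.30 |

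The interval is longer than the stay in every case, by a factor of about 1.4 to 2.0.

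**Typical rather than maximum wait.** The 26.1 weeks applies to an event just after a meeting. If events are spread evenly between meetings (an assumption), the mean wait is 26.1 / 2 = 13.0 weeks, about one nominal stay. Under the same assumption the last column is the share of events that wait longer than a full stay: 49% in the nominal case and 30% in the longest. If enrolment dates are spread evenly, it is also the share of participants whose entire stay falls between two consecutive reviews.

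**Stopping wording, side by side.** The early-stopping sentence is permissive and does not say that it is the only ground for such a recommendation. The preceding sentence covers any monitoring finding, and the bullet on suitable action covers any safety matter. Section 15.0 treats falls as a known risk. Taken together, the narrow sentence and the wide ones do not match in scope, but none of them forbids action.

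**The case against.** The strongest defence is that the arrangement is coherent as it stands. The IRB hears of every SAE at once, the investigator may withdraw medically unstable participants (section 14.0), the trial is single-site, and the training device applies no energy to the participant (section 3.0). Nothing forbids contact with the DSMB between meetings, and the bullet on problems raised by the principal investigator could serve for that. The DSMB also reviews a data and safety monitoring plan before enrolment. If that is a separate document, notification details may sit there, out of view. The 26 weeks is a maximum, and comparing it with one participant's stay is a benchmark chosen for this check.

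Much of this stands. The period between meetings is not unsupervised, and the lack of an expedited route to the DSMB is an inference from silence. What remains is that the text sets immediate timing for one body and review timing for the other, and that the investigator channel has neither timing nor an SAE trigger.

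Three stronger readings are tempting and are not supported:
- *That the DSMB could not recommend stopping over falls because they are anticipated.* The wider sentences let it act on any monitoring finding. A run of falls despite a harness meant to prevent them could itself fairly be called an unanticipated concern.
- *That non-serious falls have no route to anyone between reviews.* The investigator may raise them with the DSMB. The timing is missing, not the route.
- *That the gap can be expressed as a number of participants or training sessions exposed to falls.* The accrual period is not given, and section 3.0 limits standing and walking to those who can do so unsupported, so a count of all sessions would not measure fall exposure.

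**Conclusion.** The reporting point holds. As written, an SAE can take up to about 26 weeks to reach the DSMB, against a stay of about 13 to 18 weeks, so a participant can enrol, have an SAE and leave before the board sees it. The maximum rests only on the stated schedule. The mean wait of about 13 weeks and the shares of 30% to 49% also assume even timing between meetings. All of it assumes that no unseen monitoring plan sets a faster rule.

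This is a weakness in safety oversight that is worth correcting. It does not mean that SAEs go unreported, and it has no bearing on sample size, power or alpha.

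The stopping point holds only as an inconsistency of wording to be reconciled, not as a gap in the DSMB's authority.

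**What to change.** In section 13.0, under Reporting of safety data, state that each SAE notice goes to the DSMB chair at the same time as to the IRB, and that the chair may call an unscheduled review. Section 13.0 lists three members but names no chair, so one would have to be designated. If a separate monitoring plan already contains such a rule, a cross-reference to it is enough.

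Separately, the sponsor should reconcile the early-stopping sentence with the wider remit stated in section 13.0 and with the risks named in section 15.0. How to reconcile them is for the sponsor and the DSMB to decide.

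The cost is a few sentences of text and an occasional extra notice to, or call with, a board that already exists. Visits, outcomes and the analysis are unchanged.

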14.0 Withdrawal of Subjects

- Subjects who do not show up on scheduled visits or do not complete the intervention in 10 weeks may be withdrawn by the investigator. Subjects who are or become medically unstable may be withdrawn by the investigator.
- For those who withdraw from the research, their data collected up to that point may be used by the investigator.

15.0 Risks to Subjects

There is a slight risk for loss of confidentiality although researchers will take appropriate steps to protect any information collected about the participants. There is a minor risk of physical and mental fatigue from engaging in the study activity. There is a minor risk of discomfort from having muscle activity sensors or joint position sensors during hand movement during the behavioral hand function assessment. There is a minor risk of skin irritation from adhesives used to affix muscle activity sensors or joint position sensors during the behavioral hand function assessment. There is a risk of fall from standing or walking, although subjects will be wearing a whole body harness to prevent such events. The treatment one person receives may prove to be less effective or to have more side effects than the other study treatment. The experimental treatments may have unknown side effects.

16.0 Potential Benefits to Subjects or Others

There may be no benefit from participating in this study. The potential benefit is that the training the participant receives may help recover their hand function, although this cannot be guaranteed. The knowledge regarding the merit of force training is important to create a new therapy option for people who had a stroke and may benefit stroke survivors in general. The risks are deemed reasonable in relation to the potential gain of knowledge regarding the effect of novel force training in enhancing hand force control and hand function after stroke.

